1.5. Potential Risks and Benefits of the Treatment Regimen

INCB050465 has effects on the immune system. Therefore, subjects in this study will be monitored closely for evidence of infections or new cancers, and study treatment administration will be discontinued if there is evidence of clinically significant infection or new cancer.

Pneumocystis jirovecii pneumonia has not been reported with the use of INCB050465 as monotherapy. However, PJP was reported for 1 subject administered INCB050465 in combination with pembrolizumab in Study INCB 39110-107 (NCT02646748). All subjects in Study INCB 50465-205 will receive PJP prophylaxis. Subjects will be asked to report all sulfa drug allergies, and those allergic to standard PJP prophylaxis with sulfonamide antibiotics will receive either inhaled pentamidine or atovaquone for PJP prophylaxis; these subjects will not be given dapsone.

As presented in Section 1.3, objective responses were reported in 30 of 55 NHL subjects, including 6 responses in 9 MCL subjects. Adverse events were also observed in subjects administered INCB050465 (see Section 1.3). Dose modification guidance and supportive care guidelines for diarrhea/colitis are implemented in this study. INCB050465 monotherapy has also demonstrated efficacy in multiple tumor types including MCL (see Section 1.3).

Based on safety and efficacy data from the ongoing Study INCB 50465-101, the treatment regimen for this study will be 20 mg QD for 8 weeks, followed by either 20 mg once weekly or 2.5 mg QD of INCB050465. As detailed in Section 1.3, these regimens are proposed to assess whether the frequency of AEs leading to treatment withdrawal will be reduced while maintaining PI3K pathway inhibition and maintenance of response.

INCB050465 is metabolized primarily by CYP3A4; therefore, use of any potent CYP3A4 inhibitors or inducers within 14 days or 5 half-lives (whichever is longer) before the first dose of INCB050465 will be prohibited.

The effects of INCB050465 on fetal development have not been evaluated, nor is it known whether INCB050465 passes into human breast milk; therefore, subjects who are pregnant or breastfeeding are excluded from participation in this study.

There are no preclinical data available to date on the potential phototoxicity of INCB050465. Therefore, subjects enrolled in this study taking INCB050465 will be instructed by the site staff to take precaution to protect themselves from the sun/ultraviolet light. This includes wearing long sleeves, long trousers, hats, sunscreen, and sunglasses.

2. STUDY OBJECTIVES AND ENDPOINTS

The objectives and endpoints described in [Table 1](#) are applicable for both cohorts. See Section [9.4](#) for details on the analysis of endpoints for each cohort.

Table 1: Study Objectives and Endpoints

Objectives	Endpoints
Primary	
To assess the efficacy of INCB050465 in terms of ORR in subjects in with MCL that is relapsed or refractory after at least 1 but no more than 3 prior systemic treatment regimens.	ORR defined as the percentage of subjects with a CR or PR as determined by an IRC assessment of response according to CT-based response criteria for lymphomas (Cheson et al 2014).
Secondary	
To assess DOR.	DOR defined as the time from first documented evidence of CR or PR until disease progression or death from any cause among subjects who achieve an objective response, as determined by radiographic disease assessment provided by an IRC.
To assess CRR.	CRR defined as the percentage of subjects with a CR as defined by response criteria for lymphomas (Cheson et al 2014), as determined by an IRC.
To assess PFS.	PFS defined as the time from the date of the first dose of study treatment until the earliest date of disease progression, as determined by radiographic disease assessment provided by an IRC, or death from any cause.
To assess OS.	OS defined as the time from the date of the first dose of study treatment until death from any cause.
To assess the best percentage change in target lesion size.	Best percentage change in target lesion size from baseline, where target lesion size is measured by the sum of the product of diameters of all target lesion sizes.
To characterize the safety and tolerability of INCB050465.	Safety measured by AEs, 12-lead ECGs, chemistry and hematology laboratory values, vital signs, and physical examinations.

3. SUBJECT ELIGIBILITY

Deviations from eligibility criteria are not allowed because they can potentially jeopardize the scientific integrity of the study, regulatory acceptability, and/or subject safety. Therefore, adherence to the criteria as specified in the Protocol is essential.

3.1. Subject Inclusion Criteria

A subject who meets all of the following criteria may be included in the study:

1. Men and women, aged 18 or older.
2. Pathologically confirmed MCL, with documentation of either overexpression of cyclin D1 or t(11;14).
3. Have received at least 1 but no more than 3 prior systemic treatment regimens.
 - a. Subjects in Cohort 1 will have previously received ibrutinib.
 - b. Subjects in Cohort 2 will not have previously received a BTK inhibitor (eg, ibrutinib).
4. Documented failure to achieve at least PR with or documented disease progression after the most recent treatment regimen.
5. Radiographically measurable lymphadenopathy or extranodal lymphoid malignancy (defined as the presence of ≥ 1 lesion that measures > 1.5 cm in the LDi and ≥ 1.0 cm in the longest perpendicular diameter as assessed by CT or MRI).
6. Subjects must be willing to undergo an incisional, excisional, or core needle lymph node or tissue biopsy or provide a lymph node or tissue biopsy from the most recent available archival tissue.
7. Life expectancy > 3 months.
8. ECOG performance status 0 to 2 (see [Appendix B](#)).
9. Adequate hematologic, hepatic, and renal function (values must not be achieved with growth factors):
 - a. ANC $\geq 1.0 \times 10^9/L$.
 - b. Hemoglobin ≥ 8.0 g/dL.
 - c. Platelet count $\geq 50 \times 10^9/L$.
 - d. Total bilirubin $\leq 1.5 \times ULN$. Subjects with documented history of Gilbert's syndrome and in whom total bilirubin elevations are accompanied by elevated indirect bilirubin are eligible.
 - e. ALT/AST $\leq 3.0 \times ULN$ or $\leq 5 \times ULN$ in the presence of liver metastases.
 - f. Calculated creatinine clearance ≥ 50 mL/min by the Cockcroft-Gault Equation ([Cockcroft and Gault 1976](#)) or the estimated glomerular filtration rate ≥ 50 mL/min/1.73 m² using the Modification of Diet in Renal Disease formula.

10. Willingness to avoid pregnancy or fathering children based on the criteria below:
- Woman of nonchildbearing potential (ie, surgically sterile with a hysterectomy and/or bilateral oophorectomy OR ≥ 12 months of amenorrhea and at least 45 years of age).
 - Woman of childbearing potential who has a negative serum pregnancy test at screening and who agrees to take appropriate precautions to avoid pregnancy (with at least 99% certainty) from screening through safety follow-up. Permitted methods that are at least 99% effective in preventing pregnancy (see [Appendix A](#)) should be communicated to the subject and their understanding confirmed.
 - Man who agrees to take appropriate precautions to avoid fathering children (with at least 99% certainty) from screening through at least 93 days after the last dose of study treatment. Permitted methods that are at least 99% effective in preventing pregnancy (see [Appendix A](#)) should be communicated to the subject and their understanding confirmed.

3.2. Subject Exclusion Criteria

A subject who meets any of the following criteria will be excluded from the study:

- History of central nervous system lymphoma (either primary or metastatic).
- Prior treatment with idelalisib, other selective PI3K δ inhibitors, or a pan-PI3K inhibitor.
- Allogeneic SCT within the last 6 months, or autologous SCT within the last 3 months before the date of the first dose of study treatment.
- Active graft-versus-host disease.
- Use of immunosuppressive therapy within 28 days of the date of study treatment administration. Immunosuppressive therapy includes, but is not limited to, cyclosporine A, tacrolimus, or high-dose corticosteroids. Subjects receiving corticosteroids must be at a dose of ≤ 10 mg/day prednisone (or equivalent) within 7 days of the date of first study treatment administration.
- Receipt of anticancer medications or investigational drugs within the following intervals before the first dose of study treatment:
 - < 10 weeks from completion of any radio- or toxin-immunoconjugates.
 - < 6 weeks for mitomycin-C or nitrosoureas.
 - < 4 weeks for immunotherapy.
 - < 3 weeks for radiotherapy.
 - < 3 days for ibrutinib.
 - < 2 weeks for any investigational agent or other anticancer medications.
- Inadequate recovery from toxicity and/or complications from a major surgery before the date of the first dose of study treatment.
- Prior treatment-related toxicities have not resolved to NCI CTCAE v4.03 ([NCI 2010](#)) \leq Grade 1 before the date of the first dose of study treatment except for stable chronic toxicities (Grade ≤ 2) not expected to resolve (eg, stable Grade 2 peripheral neurotoxicity).

9. Concurrent anticancer therapy (eg, chemotherapy, radiation therapy, surgery, immunotherapy, biologic therapy, hormonal therapy, investigational therapy, or tumor embolization).
10. Use or expected use during the study of any prohibited medications, including potent CYP3A4 inhibitors or inducers (please refer to the Pharmacy Manual and consult your local pharmacist) within 14 days or 5 half-lives (whichever is longer) before the date of study treatment administration.
11. Significant concurrent, uncontrolled medical condition, including, but not limited to, renal, hepatic, hematological, GI, endocrine, pulmonary, neurological, cerebral, or psychiatric disease.
12. Current or previous other malignancy within 3 years of study entry, except cured basal or squamous cell skin cancer, superficial bladder cancer, prostate intraepithelial neoplasm, carcinoma *in situ* of the cervix, or other noninvasive or indolent malignancy without sponsor approval.
13. History of stroke or intracranial hemorrhage within 6 months of the date of study treatment administration.
14. Chronic or current active infectious disease requiring systemic antibiotics, antifungal, or antiviral treatment or exposure to a live vaccine within 30 days of study treatment.
15. Known HIV infection or positivity on immunoassay. Note: HIV screening test is optional for subjects enrolled in the United States, but subjects with known HIV infection in the United States will be excluded.
16. Hepatitis B (HBV) or hepatitis C (HCV) infection: Subjects positive for hepatitis B surface antigen or hepatitis B core antibody will be eligible if they are negative for HBV-DNA; these subjects should be considered for prophylactic antiviral therapy. Subjects positive for anti-HCV antibody will be eligible if they are negative for HCV-RNA
17. Clinically significant cardiac disease, including unstable angina, acute myocardial infarction, and/or cardiac conduction issues within 6 months of the date of study treatment administration.
18. Current New York Heart Association Class II to IV congestive heart failure or uncontrolled arrhythmia.
19. Presence of an abnormal ECG that is clinically meaningful. Screening QTc interval > 450 milliseconds is excluded (corrected by Fridericia). In the event that a single QTc is > 450 milliseconds, the subject may enroll if the average QTc for 3 ECGs is < 450 milliseconds.
20. Unable to swallow and retain oral medication, malabsorption syndrome, disease significantly affecting GI function, total resection of the stomach or small bowel, ulcerative colitis, symptomatic inflammatory bowel disease, or partial or complete bowel obstruction.
21. Known hypersensitivity or severe reaction to INCB050465 or its excipients (refer to the [IB](#)).

22. History of serious allergic reactions including anaphylaxis and toxic epidermal necrolysis.
23. Currently pregnant or breastfeeding.
24. Any condition that would, in the investigator's judgment, interfere with full participation in the study, including administration of study treatment and attending required study visits; pose a significant risk to the subject; or interfere with interpretation of study data.
25. Inability to comprehend or unwilling to sign the ICF (see Section 7.1).

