5.4.1.1. Dose Modifications

Dose modification guidance for AEs that have been previously observed in subjects receiving INCB050465 or are potential class-effect AEs are provided (see [Table 3](#) and [Table 5](#)). The starting dose and dose reduction levels of INCB050465 are provided (see [Table 4](#)). Individual decisions regarding dose interruption and reduction should be made using clinical judgment and in consultation with the sponsor's medical monitor, taking into account relatedness of the AE to the study treatment and the subject's underlying condition. Adverse events that have a clear alternative explanation or transient (≤ 72 hours) abnormal laboratory values without associated clinically significant signs or symptoms may be exempt from dose reduction guidelines

Table 3: Guidelines for Interruption and Restarting INCB050465

ADVERSE EVENT	ACTION
Chemistry	

 Grade 3 AST and/or ALT ($> 5.0 \times \text{ULN}$). 
Note: In subjects with liver metastasis-related elevations at baseline, contact sponsor to discuss clinical management and possible dose reductions.
	
Step 1: Interrupt INCB050465 and monitor weekly until the toxicity has resolved to Grade ≤ 1.
 
Step 2: Restart INCB050465 at next lower dose with medical monitor approval. Monitor as clinically indicated.

Hematology	

 Grade 3 ANC ($< 1.0 \times 10^9/\text{L}$) Grade 2 platelet count (50 to $< 75 \times 10^9/\text{L}$) for subjects who enrolled with platelets $> 100 \times 10^9/\text{L}$. Grade 3 platelet count ($< 50 \times 10^9/\text{L}$) for subjects who enrolled with platelets $\leq 100 \times 10^9/\text{L}$. 	
Step 1: Interrupt INCB050465 up to 14 days until the toxicity has resolved to Grade ≤ 1 or pretherapy baseline. For Grade 3 ANC, monitor at least weekly.
 
Step 2: Restart INCB050465 at same dose; monitor as clinically indicated.

 Grade 4 ANC ($< 0.5 \times 10^9/\text{L}$). Grade 3 or Grade 4 febrile neutropenia. Platelet count is Grade 4 ($< 25 \times 10^9/\text{L}$). 	
Step 1: Interrupt INCB050465 up to 14 days until the toxicity has resolved Grade ≤ 2. (Monitor at least weekly.)
 
Step 2: Restart INCB050465 at same dose. Monitor as clinically indicated. If recurs, restart at next lower dose.

Other toxicities	

 Diarrhea/colitis. 	See Table 5 .

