5.4.4. Definition for Immune-Related Adverse Events

Adverse events of a potential immunologic etiology, or irAEs, may be defined as an AE consistent with an immune phenomenon associated with study treatment exposure after all other etiologies have been eliminated. Immune-related AEs may be expected based on previous experience with INCB050465. Special attention should be paid to AEs that may be suggestive of potential irAEs. Based on emerging data from the ongoing Study INCB 50465-101, most irAEs occur after the first 9 weeks of study treatment administration. However, an irAE could occur at any time. Suspected irAEs should be discussed with the medical monitor when possible.

Subjects should receive appropriate supportive care measures as deemed necessary by the treating investigator. Suggested supportive care measures for the management of drug-related AEs with potential immunologic etiology are outlined in Table 3 and Section 5.4.1. For each

AE, attempts should be made to rule out other causes, including but not limited to metastatic disease or bacterial or viral infection, which might require specific supportive care.

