- ^e Height required at screening only.
- ^f Timed triplicate ECGs will be obtained during the Day 1 visit (predose) and Week 4 visit (predose and 1.5 hours [\pm 15 minutes] after receiving study treatment).
- ^g Required at baseline except for reasons provided in Section 7.6.2.
- ^h If disease is present in bone marrow at baseline, a bone marrow biopsy will be required to confirm CR or may be performed as clinically indicated.
- ⁱ PJP prophylaxis should be given while subjects are receiving study treatment and continue for at least 2 to 6 months after the last dose of study treatment.
- ^j May be conducted by clinic visit, telephone, or email.

Table 7: Schedule of Laboratory Assessments

Laboratory Tests ^a	Section	Screening	Treatment				EOT	Safety Follow-Up
		Day -28 to -1	Day 1 ^b	Every 4 Weeks Through Week 48 (± 3 Days)	Every 12 Weeks From Week 48 (± 1 Week)	Other		EOT + 30-35 Days
Serum chemistries	7.5.7.1	X	X ^c	X	X		X	X
Hematology ^d	7.5.7.1	X ^e	X ^c	X	X	X ^f	X	X
Serology	7.5.7.3	X		X ^g	X ^g			
HIV testing	7.5.7.3.1	X ^h						
Serum pregnancy	7.5.7.2	X ⁱ					X	
Urine pregnancy	7.5.7.2					X ^j		
Tumor biopsy	7.8.5	X ^o				X ^p		

^a All laboratory assessments must be performed at a central laboratory, unless otherwise specified (see Section 7.5.7).

^b All laboratory assessments are to be performed before administration of study treatment on Day 1, unless otherwise specified.

^c If chemistry and/or hematology laboratory assessments occurred in the preceding 7 days, Day 1 assessments may be omitted.

^d Hematology samples will be collected every 2 weeks for the first 8 weeks.

^e Beta-2 microglobulin testing will be done at screening only.

^f Week 2 and Week 6 (± 3 days).

^g Samples for CMV DNA analysis only.

^h Optional for subjects enrolled in the United States.

ⁱ Only for females of childbearing potential; negative serum pregnancy test must be obtained within 14 days before administration of study treatment. Screening test may be performed centrally or at the investigative site laboratory.

^j Only for females of childbearing potential; if a urine pregnancy test is positive, then a serum pregnancy test should be performed. Urine pregnancy must be collected every 4 weeks until last dose of study treatment.

[REDACTED]

Table 8: Laboratory Tests: Required Analytes

Serum Chemistries	Hematology	Serology

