Albumin Alkaline phosphatase ALT AST Bicarbonate Blood urea nitrogen C-reactive protein Calcium Chloride Creatinine Glucose Lactate dehydrogenase Phosphate Potassium Sodium Total bilirubin Direct bilirubin (if total bilirubin is > ULN) Total protein Uric acid Beta-2 microglobulin ^a	Complete blood count, including: Hemoglobin Hematocrit Platelet count (absolute) Red blood cell count White blood cell count Differential count, including: Basophils Eosinophils Lymphocytes Monocytes Neutrophils Absolute values must be provided for WBC differential laboratory results: Lymphocytes Neutrophils	Hepatitis B surface antigen Hepatitis B surface antigen antibody Hepatitis B core antibody HBV-DNA HCV antibody HCV-RNA CMV DNA HIV antibody (immunoassay) ^b 
Pregnancy Testing
 Only for female subjects of childbearing potential. Pregnancy tests (serum or urine) should be repeated if required by local regulations.

Note: Additional tests may be required, as agreed by investigator and sponsor, based on emerging safety data.

^a Beta-2 microglobulin testing will be performed at screening only.

^b Optional for subjects enrolled in the United States.

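### Subjects with hepatitis B markers enter on one negative HBV-DNA, but the visible schedule never repeats the test and restart after Grade 3 ALT/AST does not require it

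*Protocol*

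**What the plan says.** **Entry.** Protocol Section 3.2, criterion 16 (also in the Synopsis): subjects with HBsAg or anti-HBc "will be eligible if they are negative for HBV-DNA; these subjects should be considered for prophylactic antiviral therapy". Appendix E, Amendment 2, gives two reasons for this criterion: no reactivation had been reported in Study INCB 50465-101, and the change aligns with approved PI3K inhibitors.

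**Testing.** Table 8 puts HBV-DNA in the serology panel ("HBV-DNA HCV antibody HCV-RNA CMV DNA"). Table 7 schedules serology at screening. Both on-treatment serology marks carry footnote g: "Samples for CMV DNA analysis only". The serology row has no mark at EOT or safety follow-up, and Section 7.5.7.3 adds no further hepatitis B schedule.

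**Management.** For Grade 3 AST/ALT (above 5 x ULN), Table 3 says "Interrupt INCB050465 and monitor weekly until the toxicity has resolved" to Grade 1 or lower, then "Restart INCB050465 at next lower dose with medical monitor approval". It has rows for PJP, CMV and varicella zoster infection but none for hepatitis B.

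**General safeguards.** Section 1.5: "study treatment administration will be discontinued if there is evidence of clinically significant infection or new cancer". Section 5.4.4, on suspected immune-related events: "attempts should be made to rule out other causes, including but not limited to metastatic disease or bacterial or viral infection". Section 8.5 lists ALT and AST at or above 5 x ULN as adverse events of special interest, and the IDMC reviews safety periodically.

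**The concern.** The protocol knowingly admits subjects with evidence of hepatitis B exposure to a drug that Section 1.5 describes as acting on the immune system. The negative HBV-DNA that qualifies them is obtained once. After that, no scheduled test looks for the virus, although CMV DNA is drawn at every on-treatment visit.

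Two things are at stake. The first is timing: the scheduled sign of reactivation is an abnormal liver panel, and the interval between panels triples after Week 48. The second is attribution. When a marker-positive subject has Grade 3 ALT/AST, the decision to restart can be taken without knowing whether HBV-DNA has become detectable. SAP Section 9.3.3 (potential Hy's law events) selects cases on chemistry alone, so a listed case may have no HBV-DNA result to read it against.

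**Working it through.** The plan states no figure to reproduce. The check is a reading of the schedule followed by simple counts.

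**Step 1. Is HBV-DNA scheduled after screening?**
- Table 8 assigns HBV-DNA to serology.
- Table 7 marks serology at screening and in the two on-treatment columns. Footnote g restricts the on-treatment marks to CMV DNA.
- EOT and safety follow-up have no serology mark.
- Scheduled HBV-DNA tests after screening = 0.

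**Step 2. How many visits could carry it?** Inputs: about 14 months of treatment (Synopsis); visits every 4 weeks through Week 48, then every 12 weeks (Table 7).
- 14 x 52/12 = 60.7 weeks.
- Weeks 4 to 48: 48/4 = 12 visits. Week 60 adds 1. Total 13, each with CMV DNA.
- Chemistry falls at the same 13 visits plus EOT and safety follow-up: 13 + 2 = 15. The predose Day 1 draw, which may be omitted if chemistry was done in the preceding 7 days, is not counted; including it gives up to 16.

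**Step 3. How far apart are the liver panels?** Windows from Table 7: ±3 days through Week 48, ±1 week after.

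| Interval | Nominal (days) | Longest with windows (days) |
|---|---|---|
| Visits up to Week 48 | 28 | 28 + 3 + 3 = 34 |
| Week 48 to Week 60 | 84 | 84 + 3 + 7 = 94 |
| Later visits | 84 | 84 + 7 + 7 = 98 |

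The 98-day gap first arises between Weeks 60 and 72, beyond the expected 14 months, so it applies only to subjects treated for longer than that.

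**Step 4. What does a raised ALT/AST trigger?** Table 3 acts at Grade 3. Unless otherwise specified, Grade 1 or 2 toxicity is treated while dosing continues, and other Grade 4 toxicity leads to discontinuation unless the sponsor approves an exception. None of these rows names an HBV-DNA test. Restart after Grade 3 has two conditions: resolution to Grade 1 or lower, and medical monitor approval.

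**Step 5. How much does the Study 101 experience say?** The upper one-sided 95% bound for 0 events in n exposed subjects is 1 - 0.05^(1/n). Section 1.3 reports 72 subjects at the August 2017 cutoff, but the documents do not say how many had hepatitis B markers. The values of n below are therefore assumptions.
- n = 72 (every subject exposed): 4.1%
- n = 10: 25.9%
- n = 5: 45.1%

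Without the number exposed, the absence of reported reactivations sets no useful limit on the risk in marker-positive subjects.

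**The case against.** The best reply is that existing provisions already cover this. Liver panels are frequent in the first 48 weeks and include bilirubin as well as ALT and AST. Grade 3 ALT/AST brings interruption and weekly monitoring, and the medical monitor decides on restart. Table 8 allows additional tests, Section 6.6 allows unscheduled visits, and the Section 1.5, 5.4.4, 8.5 and IDMC provisions all apply. Section 1.3 reports no liver function abnormality above Grade 1 on treatment among the 72 Study 101 subjects, so a Grade 3 event here would stand out and prompt questions.

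Most of this stands and it limits the point. None of it requires an HBV-DNA result, though: each provision either waits for a clinical or chemical sign or leaves the test to judgement. The clean liver record is relevant, but the number of marker-positive subjects behind it is unknown.

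A second reply is that Amendment 2 uses Study 101 to justify eligibility, not to argue that repeat testing is unnecessary. That is correct; the amendment simply leaves monitoring unaddressed.

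A third is that parts of Table 7 and of the Amendment 2 log are redacted, and the Laboratory Manual and Investigator's Brochure are not available. A hidden HBV-DNA schedule cannot be excluded, but it is unlikely because HBV-DNA belongs to the visible serology row.

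Stronger readings that a reader might infer are not supported:
- That the protocol permits dosing through known reactivation. Section 1.5 requires discontinuation for clinically significant infection.
- That prophylaxis should be mandatory, or that HBV-DNA is sure to give warning ahead of liver injury. The documents contain no evidence on either.

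**Conclusion.** The point holds as a gap in scheduled monitoring. Marker-positive subjects have 0 scheduled HBV-DNA tests after screening, against 13 for CMV DNA over the expected 14 months, and restart after Grade 3 ALT/AST does not depend on an HBV-DNA result. Scheduled detection rests on liver chemistry, with gaps of up to 34, 94 or 98 days depending on the period. HBV-DNA testing, and with it attribution of liver events in these subjects, is possible but not ensured.

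The practical size cannot be stated, because the documents give neither the number of marker-positive subjects nor a reactivation risk for this drug. The conclusion assumes that the redacted parts of Table 7 hold no HBV-DNA schedule, and the visit count assumes the protocol's expected 14-month treatment duration. ORR, the sample size and the futility rule are not affected. This is a low-cost safety improvement, not a flaw in the trial's inference.

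**What to change.** By protocol amendment:

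1. **Table 7.** Extend footnote g so that on-treatment serology is CMV DNA for all subjects, plus HBV-DNA for those HBsAg-positive or anti-HBc-positive at screening. Add HBV-DNA for these subjects at EOT and safety follow-up.
2. **Table 3, Grade 3 ALT/AST row.** In these subjects, require an HBV-DNA result before any restart.
3. **Table 3, new row.** If HBV-DNA becomes detectable, interrupt INCB050465, start antiviral management and contact the medical monitor. State that Section 1.5 governs discontinuation if the infection is clinically significant. Whether and when a subject may restart after detectable HBV-DNA is a clinical decision on which opinions may differ, so the row should not promise a restart.

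The cost is about 13 + 2 = 15 HBV-DNA assays per marker-positive subject over 14 months and none for other subjects. All 15 fall on scheduled chemistry draws and 13 of them on scheduled CMV DNA draws, so no visit is added. Any HBV-DNA result required before a restart outside these visits would be extra.
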